9.4.4 Safety Analyses

The primary outcome is summaries by arm of the cumulative incidence of SAE, as described in [Section 8.4.2](#). Safety endpoints include death through Day 29, SAEs, discontinuation of study drug infusions, and Grade 3 and 4 AEs. Safety events will be analyzed as individual events and as part of a composite endpoint (e.g. any SAE). Proportions at specific study time points and by arm, e.g. Day 15, 22, 29 and 60, will be tabulated, as well as a Kaplan-Meier curve for death and time to first event for the composite endpoint. Each AE will be counted once for a given participant and graded by severity and relationship to COVID-19 or study intervention. AEs will be coded using the current version of the Medical Dictionary for Regulatory Activities (MedDRA). AEs will be presented by system organ class, duration (in days), start- and stop-date. Adverse events leading to premature discontinuation from the study intervention and serious treatment-emergent AEs will be summarized. Analyses will be primarily descriptive.

Events that would result in immediate study pause for DSMB review and the potential stopping of the study include: transfusion reactions or coagulopathic events. Plasma transfusion is a safe and commonly used treatment and so we do not anticipate additional SAE, above what these critically ill patients would experience as part of their baseline risk.

9.4.5 Baseline Descriptive Statistics

Baseline characteristics will be summarized for the treatment and control groups. For continuous measures, the mean and standard deviation will be summarized. Categorical variables will be described by the number and proportion in each category. Of interest will be participant demographics, e.g. age, gender, race, as well as clinical and laboratory variables describing co-morbidities and disease severity at baseline. P-values for significance testing between groups, e.g., Fisher's exact test for proportions or Wilcoxon Rank Sum for continuous, will be considered but differences between groups interpreted primarily qualitatively.

9.4.6 Planned Interim Analyses

A Data Safety Monitoring Board (DSMB) will monitor ongoing results to ensure participant well-being and safety as well as study integrity. The DSMB will be convened for a detailed review of safety data after 10 patients have been enrolled and reached day 15 or at 2 months, whichever comes first, and then as needed. No formal statistical interim analyses are planned. Events that would result in immediate study pause for DSMB review and the potential stopping of the study include: transfusion reactions or coagulopathic events. Plasma transfusion is a safe and commonly used treatment and so we do not anticipate additional SAE, above what these critically ill patients would experience as part of their baseline risk.

The study team will provide the DSMB Committee reports of enrollment, baseline characteristics, follow-up rates, and safety data.

9.4.7 Sub-Group Analyses

Subgroup analyses for the primary and key secondary efficacy outcomes will be considered to see where the differences between the treatment and control groups varied across the following subgroups: age, sex, and duration of symptoms prior to enrollment. A forest plot will display confidence intervals across subgroups. We do not expect to have enough sample size to conduct formal interaction tests to determine whether the effect of treatment varies by subgroup.

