9.2 Sample Size Determination

A total of 80 participants are expected to enroll and be randomized in a 1:1 fashion to one of two study arms. Sample sizes are determined by desire to estimate safety and to provide a preliminary idea of efficacy. Given patients will be hospitalized at enrollment, we expect very low missing data rates for early safety and efficacy endpoints. We also expect to be able to have good follow-up post discharge until the end of the study. Patients will be analyzed for safety if they receive at least one dose of the experimental treatment. For efficacy endpoints, analyses will be according to the intent-to-treat principle and outcomes on all enrolled participants will be included for analysis. All power calculations assume Type I error rate of alpha=0.05. Power calculations were done using STATA/SE v16.0.

With a sample size of 40 for a given arm, the expected probability of observing zero or at least one adverse event at varying underlying adverse event rates under a binomial distribution is shown below in Table 3. At this sample size, it is likely to see at least one person with an adverse event even with relatively small rates of adverse reactions. For example, 40 individuals in one arm, there is an 80% chance of observing at least one individual with an event if the underlying AE rate is 4%. The analysis of AE rates will primarily be descriptive due to the lack of power to make formal comparisons with the control arm.

Table 3. Probability of detecting zero individuals or at least one individual with an Adverse Event (AE) for a variety of different underlying AE rates and sample size N =40

AE rate	Pr(0 events)	Pr(1+ event)
0.001	0.96	0.04
0.005	0.82	0.18
0.01	0.67	0.33
0.02	0.45	0.55
0.03	0.30	0.70
0.04	0.20	0.80
0.05	0.13	0.87
0.10	0.01	0.99

While the sample size is driven by safety considerations, we also consider the operating characteristics of the proposed sample size for the analysis of the primary and secondary efficacy endpoints. The primary efficacy outcome is a comparison of the clinical severity score. The severity score is based on

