a procedure by Shaw and Fay 2016 [21], which ranks all survivors better than non-survivors, individuals with shorter recovery times as better, individuals with shorter times to death as worse, and non-recovered survivors ranked according to their Day 29 severity score. We considered the power to reject the null hypothesis that there is a 50-50 chance that the individuals receiving the experimental treatment had lower severity compared to the control arm. The analysis of the Win Ratio [22], which simply ranks the experimental participant with a matched control participant as either better or worse by considering the time to death, if evaluable, and otherwise considers the patient ranking according to the time to recovery, or time to Day 29 severity score if not-recovered, and reduces to a simple binomial proportion. For 40 matched experimental-control pairs, we have over 80% power to reject the null proportion= 50% if the experimental treatment is associated with a 80% or higher probability of having better severity than a control participant. The proposed analysis for this endpoint, described in the previous section, is expected to have even better power by also considering the timing of the event and not just the binary outcome of better or worse [21].

One can also consider the power to detect a difference in the secondary survival and recovery time endpoints. Given the sample size of 40 per arm, only very large differences would be detectable with 80% power. For example, we will have about 80% power to detect a difference between arms if the underlying event rate was 0.50 vs 0.80. Power calculations rely on the Pearson's chi-squared test approximation; log-rank statistics provided similar power to detect a hazard ratio of about 0.30.

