9.4 Statistical Analyses

9.4.1 General Approach

Descriptive statistics (mean, standard deviation, minimum, median interquartile range, and maximum values for continuous variables; and frequencies and percentages for categorical variables) will be computed for all study variables for the above populations. Unless otherwise specified, a complete case analysis will be considered such that missing values will not be replaced, and calculations will be done on available reported values. If there is a substantial amount of missing data we may consider imputation methods and adjust the analyses accordingly. Analyses will primarily be descriptive; estimates will be presented with 95% confidence intervals. Any significance testing will be done at the 0.05 level. Details for the primary and key secondary analyses are provided below. A formal Statistical Analysis Plan (SAP) will be developed prior to performing analyses of the study endpoints.

9.4.2 *Analysis of the Primary Endpoint(s)*

The primary safety endpoint is cumulative incidence of serious adverse events (SAEs) at Day 29, calculated separately by arm as the percent of individuals who had at least one SAE by Day 29. The SAE rate at all other time points of the study will also be calculated. The overall SAE incidence will be presented, as well as separately by system organ class and preferred term groupings. Percentages will be based on the number of participants who were treated (the safety analysis set). Additional frequencies will be presented with respect to maximum severity and to relationship to COVID19 and study product. Multiple occurrences of the same AE will be counted only once according to the highest occurring grade and relationship to study product/COVID19.

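### Section 9.4.7 looks for variation in the treatment effect using within-subgroup intervals only; adding the between-subgroup difference with its 95% CI would be a cheap improvement

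*Combined protocol and SAP*

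**What the plan says.** Section 9.4.7 says that subgroup analyses are to be considered for the primary efficacy outcome and for the key secondary ones. Their purpose is given as "to see where the differences between the treatment and control groups varied across the following subgroups". The three factors are age, sex and symptom duration before enrolment. The display is given in one sentence: "A forest plot will display confidence intervals across subgroups". The section then closes: "We do not expect to have enough sample size to conduct formal interaction tests to determine whether the effect of treatment varies by subgroup".

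It gives no cut-points for age or symptom duration and no expected sex split. It describes no contrast between subgroups and gives no caution about how the plot should be read.

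Section 9.4.1 calls the analyses primarily descriptive, says that "estimates will be presented with 95% confidence intervals", and leaves a formal SAP to be written before the endpoints are analysed. The supplied document contains no separate SAP text on subgroups.

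**The concern.** Whether an effect varies between two subgroups is a question about the difference between two effects. Two separate intervals do not answer it, because one can exclude no effect and the other include it when the true effects are identical. Low power is a good reason not to rely on an interaction test. It is not a reason to leave out the estimate and its interval, because the width of that interval is what tells the reader how little the data can say.

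The stake is how the results are used later. Section 4.2 shows that planning of future confirmatory studies shaped the choice of allocation ratio. Section 2.2.2 reports that good outcomes in SARS were more frequent with early plasma. A forest plot in which only the short-duration group excluded no effect would therefore look plausible and could shape eligibility in a later trial. Nothing described in Section 9.4.7 would show that such a pattern is common under a uniform effect.

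**Working it through.** **Inputs from the plan.**
- Size: "A total of 80 participants are expected to enroll and be randomized in a 1:1 fashion to one of two study arms", so 40 per arm (Section 9.2).
- Alpha: "All power calculations assume Type I error rate of alpha=0.05". Sidedness is not stated; two-sided is assumed.
- Key secondary illustration: "we will have about 80% power to detect a difference between arms if the underlying event rate was 0.50 vs 0.80", where "Power calculations rely on the Pearson's chi-squared test approximation".
- Primary endpoint: over 80% power with 40 matched pairs at a win probability of 0.80 (Section 9.2).

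**Assumption.** Each factor splits the sample into equal halves, about 20 per arm in each.

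**1. Reproduce the plan's figure.** For 0.50 vs 0.80 with 40 per arm, the pooled proportion is 0.65.
- Null SE = √(2 × 0.65 × 0.35 / 40) = 0.1067.
- Alternative SE = √((0.25 + 0.16) / 40) = 0.1012.
- Power = Φ((0.30 − 1.96 × 0.1067) / 0.1012) = 81.6%, which agrees with the stated figure of about 80%.

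**2. Power in one half.** With 20 per arm the SEs become 0.1508 and 0.1432, and power = Φ((0.30 − 1.96 × 0.1508) / 0.1432) = 51.2%. For an effect with exactly 80% overall power, whose noncentrality is 2.80, the half-sample power is Φ(2.80/√2 − 1.96) = 50.8%.

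**3. Chance that exactly one half is significant in favour of plasma.** The halves are independent, so with power q in each the chance is 2q(1 − q).
- At q = 0.508: 2 × 0.508 × 0.492 = 50.0%.
- At q = 0.512: also 50.0%.
- With 20 per arm at 0.50 vs 0.80, an exact chi-squared calculation gives 49.8%, a Wald interval 48.5% and Fisher's test 48.4%.

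The function 2q(1 − q) peaks at q = 0.5, so 50% is the ceiling for equal halves.

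**4. Dependence on the size of the uniform effect (equal halves).**

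| Overall power | Power per half | Exactly one half significant |
|---|---|---|
| No effect (2.5% in favour) | 2.5% | 4.9% |
| 20% | 12.1% | 21% |
| 50% | 28.3% | 41% |
| 80% | 50.8% | 50% |
| 90% | 63.0% | 47% |
| 99% | 85.8% | 24% |

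At 80% overall power, unequal splits give 51% (60:40), 55% (70:30) and 61% (80:20).

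**5. Primary endpoint at its own planning effect, win probability 0.80.**
- Matched pairs: an exact binomial test with 40 pairs rejects at 27 or more wins and has 98.1% power, consistent with the stated figure of over 80%. With 20 pairs power is 80.4%, so the chance is 2 × 0.804 × 0.196 = 31.5%.
- Unmatched Mann-Whitney, 20 per arm, normal shift assumed: simulated power is 94.2%, so the chance is 2 × 0.942 × 0.058 = 11%.

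**6. Precision of the missing contrast.** For m per arm, the win-probability SE under no effect is √((2m + 1) / (12m²)).
- Overall, m = 40: 0.0650, so the 95% half-width is 0.13.
- One half, m = 20: 0.0924, half-width 0.18.
- Difference between halves: √2 × 0.0924 = 0.1307, half-width 0.26.

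The contrast between equal halves has twice the SE of the overall effect. Its power is therefore Φ(2.80/2 − 1.96) = 29% for an interaction as large as an overall effect that has 80% power. The plan is right that a formal test would be underpowered.

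**The case against.** The strongest reply is that little depends on this. The trial is an 80-person, open-label phase 1 study sized on safety. Subgroup analyses are only to be considered, all analyses are primarily descriptive, and no decision in the protocol depends on a subgroup. Section 9.4.7 itself admits the sample limitation, and a forest plot shows imprecision. A contrast known to within about ±0.26 in win probability would seldom separate anything. Most of this stands, and it makes the point minor.

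Three stronger readings are tempting, and the documents do not support them:

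- A reader might infer that a uniform benefit always carries about a 50% chance of discordant halves. It does not. The figure needs about 80% overall power, and the equal split is assumed because no cut-points are given. At the primary endpoint's own planning effect the range is about 11% to 32%.
- A reader might infer that the plan rules out an interaction estimate. It says only that formal tests are not expected to be feasible. It is silent on an estimate, and the SAP still to be written could add one.
- A reader might infer that the investigators intend to label subgroups as responders by significance. No section says so.

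What the reply does not meet is that no section supplies the contrast or a caution against comparing significance between subgroups. Being descriptive is no reason to omit the contrast, since a descriptive estimate with its interval is all that is asked for.

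**Conclusion.** The point holds as a minor one, a cheap improvement. Section 9.4.7 asks where the effect varied but does not plan the estimate that would answer this. For a uniform effect with about 80% overall power and an equally split factor, the chance per factor that exactly one half is significant is about 50%. It falls for smaller or much larger effects, to about 5% with no effect.

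These figures rest on a two-sided 0.05 level, independent halves and equal splits. The Mann-Whitney figure also rests on a normal shift. The case for the contrast does not depend on the exact percentage, because discordant intervals under a uniform effect are common over a wide range of plausible effects.

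**What to change.** Replace the last sentence of Section 9.4.7 with:

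> Formal interaction tests will be underpowered. For each factor, the difference between subgroup effects will be reported descriptively with a 95% CI beside the forest plot (difference in win probability for the primary score; ratio of hazard ratios for survival and recovery). No subgroup claim will rest on one subgroup's interval excluding no effect while another's does not.

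Cut-points for age and symptom duration could be fixed in the SAP at the same time.

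The cost is one extra column computed from data already collected, with no added participants or assessments. The downside is that the intervals will be wide, about ±0.26 in win probability for equal halves, which is an accurate picture of what 80 participants can show.

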9.4.8 Tabulation of Individual Participant Data

The time course of participants clinical and laboratory markers will be considered. Frequency of evaluation varies across clinical and laboratory assessments. Adverse event and clinical evaluation will occur daily while individual is in hospital and otherwise include Day 15, 22, 29, and 60. Laboratory measures will generally occur at days 3, 5, 8 and 11 while participant is in hospital. The full list of evaluations are shown in the Schedule of Activities (Appendix 12.1).

9.4.9 Exploratory Analyses

We will analyze a number of biomarkers of immune response and virologic efficacy. Binary proportions will be estimated along with Clopper-Pearson 95% confidence intervals. Continuous endpoints will be summarized with means, SD and normal 95% confidence intervals; for skewed data, non-parametric statistics, such as the median and interquartile range will be considered. Trends over time will be assessed descriptively, as well as with linear mixed effects models if appropriate. We will also consider the clinical efficacy of convalescent plasma administration as compared to active drug (e.g., Remdesivir) recipients in DMID Protocol Number: 20-0006. Analysis of all comparative endpoints will be similar to that for the comparison of the treatment and control groups, as described in Section 9.4.3. Further details will be provided in the SAP.

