3.3 Exploratory Objectives and Endpoints

OBJECTIVES	ENDPOINTS (OUTCOME MEASURES)
Exploratory	
Evaluate the clinical efficacy of convalescent plasma administration as compared to active drug (e.g., Remdesivir) recipients in DMID Protocol Number: 20-0006 or other relevant COVID-19 Protocols	
 • Clinical Severity 
 ○ Ordinal scale: 
 ■ Time to recovery, defined by time to levels 1-3 on the ordinal scale ■ Time to an improvement of one category and two categories from Day 1 using an ordinal scale. ■ Participant clinical status using ordinal scale at Days 3, 5, 8, 11, 15, 22, and 29. ■ Mean change in the ordinal scale from Day 1 to Days 3, 5, 8, 11, 15, 22, and 29.

 ○ National Early Warning Score (NEWS): 
 ■ Time to discharge or to a NEWS of ≤ 2 and maintained for 24 hours, whichever occurs first ■ Change from Day 1 to Days 3, 5, 8, 11, 15, and 29 in NEWS. 	NEWS assessed daily while hospitalized and on Days 15 and 29.

 ○ Oxygenation: 
 ■ Oxygenation free days to Day 29. ■ Incidence and duration of new oxygen use during the study. 	Days of supplemental oxygen (if applicable)

 ○ Non-invasive ventilation/high flow oxygen: 
 ■ Non-invasive ventilation/high flow oxygen - free days to Day 29. ■ Incidence and duration of new non-invasive ventilation or high flow oxygen use during the study. 	
 • Days of non-invasive ventilation (if applicable). • Days of high flow oxygen (if applicable).

 ○ Invasive Mechanical Ventilation / extracorporeal membrane oxygenation (ECMO): 
 ■ Ventilator / ECMO free days to Day 29. ■ Incidence and duration of new mechanical ventilation or ECMO use during the study. 	
 • Days of invasive mechanical ventilation (if applicable). • Days of ECMO (if applicable).

OBJECTIVES	ENDPOINTS (OUTCOME MEASURES)

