5.2 Exclusion Criteria

1. Contraindication to transfusion (e.g., severe volume overload, history of severe allergic reaction to blood products), as judged by the investigator.
2. Clinical suspicion that the etiology of acute illness (acute decompensation) is primarily due to a condition other than COVID-19
3. Receipt of other investigational therapy as a part of another clinical trial.
 - a. *Note: investigational therapies used as part of clinical care, (eg, remdesivir, hydroxychloroquine) are permissible.*

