6.3 Measures to Minimize Bias: Randomization and Blinding

Individuals will be randomized to the intervention or control arm in a 1:1 ratio. Randomization will occur in a blinded fashion using Redcap. Allocation will be determined using a permuted block algorithm with varying block sizes. We will stratify randomization based on whether or not a patient is on mechanical ventilation and on [remdesivir](#) at baseline. Though the intervention will not be blinded, we will attempt to minimize bias by blinding study personnel, such as individuals running laboratory assays, to the extent that it is possible.

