The primary efficacy endpoint is the clinical severity score and will be calculated based on all randomized individuals (the intent-to-treat set). The key parameter of interest will be the comparison of clinical severity between individuals receiving the experimental intervention versus control, as measured by a clinical severity score that takes into account the survival time, recovery time, and Day 29 severity score for survivors who had not recovered by Day 29. Recovery is defined by time to reaching levels 1-3 in the 8-point ordinal scale. The severity score for the primary efficacy endpoint is calculated based on a procedure proposed by Shaw and Fay 2016 [21], which ranks all survivors better than non-survivors, individuals with shorter recovery times as better, and individuals with shorter times to death as worse. Shaw and Fay 2016 showed this test statistic can be interpreted as a weighted average of the log-rank type test statistic for survival and the one for time to recovery amongst survivors. If there are participants who survive to Day 29 but have not yet recovered, their clinical severity will be determined by their Day 29 ordinal severity score, using time to reach that level to rank those who had the same Day 29 ordinal severity. It is anticipated that this analysis will have more power to detect differences than looking only at only an individual endpoint. Secondary endpoints will include a comparison of each of the individual endpoints: time to recovery and survival. Further details for the statistical analysis will be provided in the SAP

9.4.3 *Analysis of the Secondary Endpoint(s)*

Key secondary efficacy endpoints include survival and time to recovery and will generally be calculated using the intent-to-treat set. Kaplan-Meier survival curves will be calculated by arm and compared with a Peto-Peto generalized Wilcoxon test. In the event that deaths that occur, the cumulative incidence of recovery will be estimated and compared between groups using Gray's test, which will be able to capture a lower time to recovery due to either a slower event rate or a higher death rate. For interpretive purposes the cause specific hazard ratios for will also be calculated for each event type, survival and recovery, along with the Peto-Peto test. In the event of no deaths, time to recovery will be summarized with the Kaplan-Meier and compared using the Peto-Peto generalized Wilcoxon test.

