Cumulative incidence curves will be considered for time-to-event endpoints, treating death as a competing risk. Gray's test, or if the cause-specific hazard ratio was of interest the log-rank test, will be used to compare groups. Binary proportions will be estimated along with Clopper-Pearson 95% confidence intervals and compared between arms using Fisher's exact test. Continuous endpoints will be summarized with means, SD and normal 95% confidence intervals; Wilcoxon rank-sum will be used to compare arms for continuous endpoints. Ordinal endpoints (e.g. 8-point clinical severity score) will be summarized by their multinomial proportions across the different categories at Study Day 15,

22 and 29. An exact Mann-Whitney test will be used to test for whether the ordinal clinical severity was higher in one arm versus the other for ordinal endpoints. Further details for the analysis of secondary endpoints will be provided in the Statistical Analysis Plan.

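### The exploratory comparison of plasma with another trial's active-drug recipients points to unadjusted two-group methods, with no confounding control and no handling of remdesivir use among plasma recipients.

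*Combined protocol and SAP*

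**What the plan says.** Section 3.3 lists an exploratory objective to evaluate plasma "as compared to active drug (e.g., Remdesivir) recipients in DMID Protocol Number: 20-0006", and extends it to other relevant COVID-19 protocols. The same section lists a matching safety comparison. Section 9.4.9 states the method: "Analysis of all comparative endpoints will be similar to that for the comparison of the treatment and control groups", with a reference to Section 9.4.3. It closes: "Further details will be provided in the SAP".

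Section 9.4.3 names these methods:
- Kaplan-Meier curves, "compared with a Peto-Peto generalized Wilcoxon test";
- for other time-to-event endpoints, "Gray's test, or if the cause-specific hazard ratio was of interest the log-rank test, will be used to compare groups";
- binary proportions, "compared between arms using Fisher's exact test";
- Wilcoxon rank-sum for continuous endpoints and an exact Mann-Whitney test for ordinal ones;
- cause-specific hazard ratios, with no covariates named.

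On remdesivir, Section 5.2 excludes people receiving investigational therapy in another trial but notes that "investigational therapies used as part of clinical care, (eg, remdesivir, hydroxychloroquine) are permissible". Section 6.3 says "We will stratify randomization based on whether or not a patient is on mechanical ventilation" and on whether the patient is on remdesivir at baseline.

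**The concern.** Each of these methods compares two groups as they stand. Within the trial that is sound, because randomisation makes the arms comparable in expectation. Participants of another trial were not randomised against this trial's plasma arm, so nothing in the design balances severity, age, symptom duration or calendar period between them.

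Remdesivir is a second problem. If some plasma recipients also take it, the contrast is partly plasma plus remdesivir against remdesivir, and neither the objective nor Section 9 says which contrast is meant. The subgroups in Section 9.4.7 are age, sex and symptom duration, and do not include remdesivir.

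At stake is an exploratory statement about how plasma compares with an active drug. It could show a difference that is only case mix, or no difference because many plasma recipients took the same drug.

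**Working it through.** **Figures in the plan.** The plan gives no sample size, power or error rate for the external comparison, so there is no figure to reproduce. The nearest stated figure is the roughly 80% power in Section 9.2 for 0.50 vs 0.80 with 40 per arm. With a pooled proportion of 0.65, z = (0.30 × √40 − 1.96 × √(2 × 0.65 × 0.35)) / √(0.25 + 0.16) = (1.897 − 1.322) / 0.640 = 0.90, which gives 81.6% power. That agrees with the plan and does not bear on this point.

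**Is any adjustment specified?** Section 9.4.3 names no covariates, strata, matching, weighting or restriction. The only mention of adjusting analyses, in Section 9.4.1, concerns missing data. Section 6.3 balances ventilation and remdesivir within this trial only.

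**Is imbalance plausible?** The documents do not describe the external trial's case mix, so the existence and direction of an imbalance are unknown. They do show that case mix can vary:
- Section 5.1 admits ordinal levels 5 to 7.
- Section 5.5.1 says ventilated patients are also told about a single-arm plasma study when both are open, which could change the ventilated share here.
- Section 4.2 calls standard of care unclear and in flux.
- The synopsis describes a single-site study.

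**Size of a case-mix effect (illustration).** Every input except the 40 plasma participants and the 0.05 level (taken as two-sided) is assumed:
- Day 29 recovery is pN = 80% if not ventilated at baseline and pV = 40% if ventilated, the same in both trials, so there is no treatment effect.
- There are 40, 100 or 500 external participants.
- The ventilated shares are v1 (plasma) and v2 (external).

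The false difference in recovery is (v2 − v1) × (pN − pV). For 30% vs 50% it is 0.20 × 0.40 = 8 points. For 10% vs 40% it is 0.30 × 0.40 = 12 points. It scales with the assumed prognostic gap: with a gap of 20 points instead of 40, the same imbalances give 4 and 6 points.

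Rejection rates come from 8,000 simulated trials per cell (Monte Carlo standard error about 0.2 to 0.5 points). Cells show external n = 40 / 100 / 500.

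| Ventilated, plasma vs external | False difference | Fisher's exact, unadjusted | Mantel-Haenszel, stratified by ventilation |
|---|---|---|---|
| 30% vs 30% | 0 | 2.8 / 4.0 / 3.9% | 4.9 / 4.9 / 4.9% |
| 30% vs 40% | +4 points | 4.0 / 5.7 / 6.3% | 4.9 / 5.1 / 4.9% |
| 30% vs 50% | +8 points | 6.9 / 11.2 / 14.6% | 4.5 / 4.9 / 5.0% |
| 10% vs 40% | +12 points | 15.9 / 24.2 / 28.6% | 5.2 / 5.0 / 5.2% |
| 60% vs 30% | −12 points | 13.9 / 23.7 / 30.8% | 4.9 / 4.8 / 4.9% |

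Stratifying restores about 5% here because ventilation is the only confounder in the simulation. Real data would leave residual confounding.

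**Remdesivir overlap (illustration).** Assume plasma has no effect, remdesivir adds g to the recovery proportion, a share s of plasma recipients take it, and all external recipients do. The observed plasma-minus-remdesivir difference is s × g − g = −(1 − s) × g, whereas plasma without remdesivir would show −g. With g = 10 points, s = 0, 25, 50, 75 and 100% gives −10, −7.5, −5, −2.5 and 0 points. At full overlap an inert plasma looks equal to remdesivir. With g = 5 or 15 points and s = 50%, the result is −2.5 or −7.5.

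**The case against.** The strongest reply is that Section 9.4.9 is provisional. The comparison is something the trial will consider, its analysis is to be similar to Section 9.4.3 rather than identical, and details are left to a SAP whose text is not in the supplied document. Stratified or adjusted versions of the named methods are not ruled out, and cause-specific hazard ratios could carry covariates. The objective is labelled exploratory, the comparator is openly another protocol, and Section 9.4.1 already makes analyses mainly descriptive with 95% confidence intervals. On remdesivir, use at baseline is a recorded stratum, and the amendment history (Section 10.3) says it was added to allow analysis by remdesivir use.

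Much of this stands. A reader might infer that the plan commits to a biased test, or that the result will be presented as randomised evidence. The documents support neither: they specify no adjustment and defer the detail, and how readers would take the result is a prediction. A reader might also take the rejection rates as this trial's error rates. They are not, because they rest on assumed recovery rates, ventilated shares and external numbers.

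What remains is that the only direction given to the SAP author is to reuse methods chosen for a randomised comparison, and Section 9.4.1 permits testing at 0.05. An exploratory label does not remove confounding. The stated intent to analyse by remdesivir use has no matching analysis in Section 9.

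**Conclusion.** The point holds in a limited form. For a non-randomised comparison the documents point to unadjusted two-group methods, specify no confounding control, and do not separate plasma recipients with and without remdesivir. Either gap could produce or mask an apparent difference.

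On the assumed inputs, a 20- to 30-point ventilation imbalance gives a false difference of 8 to 12 points in either direction and unadjusted rejection of about 7% to 31%. A 10-point imbalance does little harm (4.0% to 6.3%). The true size cannot be determined from the documents. Materiality is low to moderate, since both primary endpoints, the randomised secondary comparisons and the sample size are untouched. The matter still deserves correction, because baseline data the trial already collects allow a better method.

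**What to change.** In Section 9.4.9, for the external comparison only, replace the statement that the analysis will be similar to Section 9.4.3 with the following:

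- An estimate with a 95% confidence interval, adjusted for or stratified by a small prespecified set of baseline factors: at least ventilation or ordinal level, and age, with symptom duration and calendar period if numbers allow. With at most 40 plasma recipients the set must stay small; weighting on many covariates could be unstable.
- A label stating that the comparison is non-randomised and exploratory.
- Results for plasma recipients with and without remdesivir at baseline shown separately, with a note that this does not remove remdesivir started later. Restricting to those without it need not be the only analysis.
- If only aggregate external data can be obtained, results shown side by side without a formal test.

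The cost is a few sentences in the protocol or SAP, a little more analysis and wider intervals. No new data collection in this trial is needed: ventilation and remdesivir at baseline are randomisation strata, and demographics, symptom onset and the ordinal score are already recorded. Access to individual external data is not established in the documents and should be confirmed first.
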